1.2 Previous Nonclinical Research and Clinical Trial Experience with Tilmanocept and Lymphoseek

A detailed evaluation of safety and efficacy data from nonclinical and clinical studies can be found in the accompanying Investigator's Brochure supplied by Cardinal. In addition, the data described in this protocol are reported in peer-reviewed publications, including nonclinical studies (Hoh et al., 2003), the Phase 1 clinical trials (Ellner et al., 2003; Wallace et al., 2007a; Wallace et al., 2007b; Wallace et al., 2003; Wallace et al., 2009), the Phase 2 clinical trial (Leong et al., 2011) and the Phase 3 studies (Tokin et al., 2012; Sondak et al., 2012; Wallace et al., 2013; Marcinow et al., 2013; Agrawal et al., 2015).

1.2.1 Nonclinical Evaluations

Nonclinical studies with Lymphoseek or tilmanocept demonstrated that the drug selectively binds to its intended receptor (the CD206 mannose binding receptor), is appropriately

distributed for radiodetection of lymphatic tissue, and is well tolerated by rats, rabbits, guinea pigs, and dogs.

Pharmacokinetics data obtained from nonclinical studies demonstrated rapid absorption into the plasma. Urinary excretion was a major pathway of elimination. Lymphoseek exhibited rapid clearance from the injection site, rapid uptake by the local lymph node, and low uptake by the remaining lymph nodes. Tilmanocept was well tolerated at all doses tested in nonclinical safety pharmacology studies and in single and repeated dose toxicology studies in rats, rabbits, and dogs. In some studies in rabbits and dogs, tilmanocept acted as a local irritant of the subcutis or skeletal muscle, and induced mild inflammation and tissue degeneration. The no-observed adverse-effect level (NOAEL) was 42 $\mu g/kg/day$. Tilmanocept was not mutagenic or genotoxic in vitro or in vivo. No signs or symptoms of hypersensitivity were observed in a study in guinea pigs.

1.2.2 Clinical Pharmacokinetics and Pharmacodynamics

In Phase 1 clinical trials, Lymphoseek showed rapid injection site clearance (approximately 2 to 3 hours). Absolute uptake in the primary sentinel lymph node was dose-related for Lymphoseek, although relative nodal uptake (%ID_{SN}) overall was independent of dose and ranged from 0.05%ID_{SN} to 1.81%ID_{SN}.

In a Phase 2 trial, Lymphoseek was highly effective in identifying tumor-draining lymph nodes (i.e., overall, a "hot spot" from Lymphoseek was identified in 93.0% of patients for whom preoperative lymphoscintigraphy was performed, and the per patient intraoperative localization rate was 96.2%). Diagnostic performance of in vivo Lymphoseek findings relative to pathology assessment of tumor tissue indicated a high per tissue sensitivity estimate (overall, 92.0%). The overall false negative rate (FNR) for pathology was 8.0%, supporting the accuracy of Lymphoseek in identifying lymph nodes with a high potential for containing tumor metastases in the lymphatics draining the tumor bed.

1.2.3 Clinical Efficacy

Clinical efficacy was evaluated in two pivotal Phase 3 clinical trials in adult subjects with breast cancer and melanoma, comparing lymph node detection of Lymphoseek and VBD. Lymphoseek demonstrated a statistically significant concordance rate with VBD (meta-analysis concordance rate = 99.99%).

The detection concordance between Lymphoseek and VBD was similar among subjects with melanoma and subjects with breast cancer (meta-analysis concordance rate = 99.99% for both populations). Lymphoseek also demonstrated a higher sensitivity for detecting tumor-positive (as confirmed by pathology) lymph nodes, corresponding to a decreased FNR when compared with VBD on a per node basis. The corresponding sensitivity rate in detection of lymph nodes most likely to be positive for tumor cells for Lymphoseek was 99.99%, compared with 78.02% for VBD. The FNR for VBD (21.98%) was higher than the FNR for Lymphoseek (0.01%). These findings suggest that, when VBD is used as the imaging agent, there is an increased risk of missing the detection of tumor-involved lymph nodes and incorrectly staging cancer patients. The Lymphoseek-only findings (pathology-positive nodes

that were hot/not blue) suggest that Lymphoseek was markedly more effective in identifying lymph nodes that harbored disease than was VBD.

A third pivotal Phase 3 clinical trial was conducted in adult subjects with oral cavity or cutaneous SCC. Subjects received an injection of Lymphoseek prior to surgery for excision of the primary tumor and Lymphoseek-guided SLN dissection followed by planned elective neck dissection. All excised lymph nodes (Lymphoseek-identified SLNs as well as non-SLNs) underwent histopathologic evaluation for presence of metastatic disease. The primary endpoint in this trial was the Lymphoseek FNR (subjects with pathology-positive lymph node(s) not identified by Lymphoseek). Thirty-nine subjects had at least one pathology-positive lymph node, and Lymphoseek detected nodes with positive pathology in all but one patient. The FNR in this trial was 2.56%.

1.2.4 Clinical Safety

More than 134,000 patients in clinical trials and US commercial use for ILM with SLNB have been exposed to Lymphoseek, and there have been no safety signals, no deaths due to drug, and no SAEs (serious adverse events) due to Lymphoseek. There are no known drug interactions leading to contraindications with the use of Lymphoseek.

1.2.5 Radiation Exposure (Subjects)

Subjects' exposure to Lymphoseek delivered as indicated in this protocol will be similar to that already established for adult breast cancer, melanoma and head/neck squamous cell carcinoma patients. The radiation absorbed dose for adults is included in the FDA-reviewed package insert for the approved product. The OLINDA (for Organ Level INternal Dose Assessment) software (Stabin et al., 2005) was used to calculate radiation exposure. For pediatric subjects, the effective dose equivalents range from 355 μ Sv (15-year-old male) to 1232 μ Sv (1-year-old female). Effective dose equivalents for pediatric subjects of various ages as well as effective dose by organ is shown in Table 1; values for adults subjects are also provided for reference.

The effective dose equivalents for other technetium 99m Tc-based evaluations in children are: 1) bone scan = 1,800 to 3,000 µSv; and 2) thyroid scan \approx 3,000 µSv.

1.2.6 Radiation Exposure (Health Care Workers and Care Givers)

Healthcare worker exposure to Lymphoseek delivered as indicated in this protocol will be similar to that already established for adult breast cancer, melanoma and head/neck squamous cell carcinoma patients. Highest whole body doses (μ Sv) received by healthcare works can be estimated for nuclear medicine staff as < 0.2, surgeons as 1.9, nurses as 0.2 and pathology staff as 2.5 such that greater than 400 procedures with Lymphoseek would have to be performed prior to reaching an annual exposure of 1000 μ Sv for non-radiation workers or greater then 20,000 procedures prior to reaching an annual exposure of 50,000 μ Sv for radiation workers.

Primary caregiver exposure has not been quantified but is assumed to be less than the exposure of providing nursing care. Excreta from patients contains very low level radiation and will effectively decay to nil in 72 hours. Patients discharged for home pose essentially no risk to their co-habitants through regulator social contact.

(Reference Patient is Intradermal Injection of Lymphoseek; Units in mGy)					
	A dult	15 Year Old	10 Year Old	5 Year Old	1 Year Old
Target Organ	Auun 70 kσ	Phantom	Phantom	Phantom	Phantom
	70 Kg	55 kg	33.5 kg	20.3 kg	12.1 kg
brain	0.003	0.0036	0.00519	0.00759	0.01119
gallbladder wall	0.0349	0.04188	0.060377	0.088297	0.130177
lower large intestinewall	0.0123	0.01476	0.021279	0.031119	0.045879
small intestine	0.0101	0.01212	0.017473	0.025553	0.037673
stomach	0.0184	0.02208	0.031832	0.046552	0.068632
upper large intestine wall	0.0125	0.015	0.021625	0.031625	0.046625
kidney	0.1863	0.22356	0.322299	0.471339	0.694899
liver	0.0324	0.03888	0.056052	0.081972	0.120852
lungs	0.0374	0.04488	0.064702	0.094622	0.139502
muscle	0.0092	0.01104	0.015916	0.023276	0.034316
ovaries	0.187	0.2244	0.32351	0.47311	0.69751
red marrow	0.0127	0.01524	0.021971	0.032131	0.047371
bone	0.0177	0.02124	0.030621	0.044781	0.066021
spleen	0.0285	0.0342	0.049305	0.072105	0.106305
thymus	0.1168	0.14016	0.202064	0.295504	0.435664
thyroid	0.088	0.1056	0.15224	0.22264	0.32824
urinary bladder	0.0586	0.07032	0.101378	0.148258	0.218578
total body	0.0195	0.0234	0.033735	0.049335	0.072735
		•			
EDE (males, mGy)	0.2960	0.3552	0.5121	0.7488	1.1040
EDE (females, mGy)	0.3302	0.3962	0.5712	0.8354	1.2316

Table 1. Estimated Radiation Absorbed Dose for a 0.5 mCi, 50 µg Dose of Lymphoseek in Intradermal Injection of Cancer Patients (Reference Patient is Intradermal Injection of Lymphoseek: Units in mGy)

2 STUDY OBJECTIVES

2.1 Primary Objective

To evaluate safety and tolerability of Lymphoseek in pediatric subjects with melanoma, rhabdomyosarcoma, or other solid tumors who are undergoing lymph node mapping.

2.2 Secondary Objectives

- To assess the excised lymph node(s) to confirm: the presence/absence of tumor metastases; agent localization per tumor type; degree of localization (nodes per subject both intraoperatively and with preoperative SPECT.
- To determine the concordance of in vivo localization rates of Lymphoseek and Lymphazurin, a vital blue dye (VBD), in tissue excised and histologically confirmed as lymph nodes from those subjects receiving two mapping agents.
- To record the change of subject stage based on histopathology and make a descriptive assessment on change in treatment plan.

3 OVERVIEW OF METHODOLOGY AND DESIGN

3.1 Overall Study Design

This is a prospective, open label, non-randomized, multicenter, blinded pathology assessment study to evaluate the tolerability and the diagnostic utility of Lymphoseek in pediatric subjects from neonatal to less than 18 years of age with melanoma, rhabdomyosarcoma, or other solid tumors where ILM and SLNB is appropriate and tumor resection or biopsy is planned. In accordance with local site practice, subjects may also receive Lymphazurin for a within-subject comparison of lymph node mapping.

The proposed study includes 3 visits: A screening visit for initial determination of eligibility and evaluation of clinical status, a baseline visit on the day of surgery, and a 4-to 14-day safety (in person) follow-up to assess subject disease management.

The Schedule of Study Events (see Appendix 1) contains a list of all study procedures and time points. Study activities are described in detail in Section 7.

3.2 Justification for Study Design and Population

This study is designed to evaluate the use of Lymphoseek as an ILM and SLNB agent in pediatric subjects with melanoma, rhabdomyosarcoma, or other solid tumors for which ILM and SLNB is useful, and by determining the concordance of detection rates of Lymphoseek and of Lymphazurin in the subjects who have utilized both agents. In addition, for each agent used, the presence or absence of tumor in the nodes, the number of nodes detected per tumor type, and the change in patient staging will be determined.

As the primary objective of this study is the safety of Lymphoseek in this population, Lymphazurin is being used to the extent possible as an optional control in this study for ILM endpoints because it would not be feasible to evaluate Lymphoseek's performance relative to another gamma-emitting radiopharmaceutical (i.e., technetium sulfur colloid) in a withinsubject study design. A meaningful comparison of radiopharmaceuticals in a between-subject design would necessitate the enrollment of large numbers of subjects, which again would not be feasible, given the relatively small incidence of pediatric solid tumors for which ILM and SLNB is indicated. Additionally, the use of Lymphazurin is a concomitant procedure that provides real-time intraoperative assessment between Lymphoseek and Lymphazurin. Lastly, Lymphazurin is an appropriate comparator because lymphatic mapping with a VBD is recognized and authorized in the US and multiple EU countries as an experiential clinical practice agent, it has been a forming agent in the development of the theory/practice of SLNB, and, importantly, its use is supported by ASCO-SSO (Wong et al, 2012) and EANM-EORTC sentinel node guidelines in melanoma (Chakera et al, 2009). However, due to the potential for allergic reactions within this vulnerable population, the use of Lymphazurin is optional and should be used consistent with instutitional practice.

3.2.1 Parent/Guardian

The subject's parent(s) or guardian(s) will assist in responding to questions and answer questions during phone calls, etc., for the duration of the study. The parent(s) or guardian(s) will accompany the study subject to the clinical appointments throughout the study and supply information as needed.

3.2.2 Rationale for Subject Selection

No clinical trials have been conducted to evaluate Lymphoseek performance in pediatric cancer patients. This study will gather feasibility and safety data in pediatric subjects diagnosed with rhabdomyosarcoma, melanoma, or other solid tumors for whom tumor resection or biopsy is planned and lymph node mapping is indicated. Melanoma and rhabdomyosarcoma represent the most frequently occurring pediatric solid tumor types for which ILM is an appropriate procedure.

3.2.3 Justification for Radiation Exposure With Proposed Lymphoseek Radioactive Dose

In nuclear medicine imaging, the diagnostic quality of an image is dependent upon the number of radioactive events (or counts) detected by the camera in the regions of interest. The number of recorded events (counts) increases with the duration of the acquisition period and, for a given acquisition period, with the radioactivity administered. Although the injected radioactivity should then be high, the higher the applied radioactivity dose, the higher the radiation exposure to the subject. Thus, in nuclear medicine, the optimal radioactive dose for a given radiopharmaceutical is usually defined as the lowest radioactive dose that renders an image of sufficient quality to provide high diagnostic confidence, commonly referred to as ALARA (as low as reasonably achievable) practices for radiation exposure.

Calculated pediatric effective dose equivalents range from 0.355 mGy (15 year old male) to 1.232 mGy (1 year old female) as as shown in Table 1 for pediatric subjects of various age.

3.3 **Protocol Adherence**

Strict adherence to all specifications laid down in this protocol is required for all aspects of the study conduct; the investigator may not modify or alter the procedures described in this protocol. If protocol modifications are necessary, all alterations that are not solely of an administrative nature require a formal protocol amendment (see Section 11.1 for the involvement of Institutional Review Board(s) (IRB).

If an investigator has deviated from the protocol in order to eliminate an immediate hazard to subjects or for other inevitable medical reasons, the investigator shall document all such deviations, including the reasons thereof, and submit the document to the sponsor and the head of the medical institution as applicable.

3.4 Study Duration

Subjects will be enrolled for approximately 1.5 months depending on the duration of the screening window (up to 30 days).

4 STUDY POPULATION

4.1 Eligibility

Subjects who fulfill all respective inclusion and none of the exclusion criteria will be eligible for enrollment into the study. All inclusion/exclusion criteria must be verified before a subject may be considered eligible for enrollment into the study. A subject will be considered enrolled in the study on the morning of study Day 1 when they arrive at the study site. Written, dated (with time noted) informed consent will be obtained from all subjects. A subject who withdraws consent prior to arrival at the study site on Day 1 will be considered a screen failure.

4.1.1 Inclusion Criteria

- 1. The subject's parent(s)/legal guardian(s) understand(s) and voluntarily signed an informed consent document prior to any study-related assessments/procedures being conducted. Where locally applicable, the subject also understands and voluntarily provides his/her assent prior to any study-related assessments/procedures being conducted.
- 2. Subject has been diagnosed with melanoma, rhabdomyosarcoma, or other tumor where tumor resection or biopsy is planned and lymph node mapping is appropriate.
- 3. The subject is clinically node negative (cN0) at the time of screening.
- 4. Age < 18 years
- 5. Male subjects of childbearing potential must be willing to use a condom during sexual intercourse and shall not father a child during the course of the study or will practice complete abstinence while on study.
- 6. Female subjects of childbearing potential must agree to the use of two physicianapproved contraceptive methods simultaneously or practice complete abstinence while on study.

4.1.2 Exclusion Criteria

- 1. The subject has had preoperative radiation therapy.
- 2. Has had previous surgery or radiation to node basins that would be involved in the ILM procedure.
- 3. Has a known allergy to dextran or VBD (if intended to be used).
- 4. Has a history of alcohol abuse or alcohol dependency in the 3 years before study entry, or is an alcoholic or drug addict, as determined by the investigator.
- 5. Before the administration of Lymphoseek has received any radiopharmaceutical within 7 radioactive half-lives of that radiopharmaceutical.

4.1.3 Justification of Selection Criteria

Rhabdomyosarcoma and melanoma represent the most frequently occurring pediatric solid tumor types for which ILM is an appropriate procedure. While most cases are expected to occur in children greater than 2 years of age, younger children who present with these tumor types and meet the other eligibility criteria will not be excluded.

4.2 Recruitment

Subjects will be recruited in accordance with the inclusion and exclusion criteria listed above from oncology or pediatric practices. Potentially suitable subjects will be asked by their treating specialist about their willingness to participate in this study. At least 20 of the recruited subjects will be ≤ 16 years of age.

The minimum number of subjects who will be recuited for each age range are indicated in Table 2.

Age Range	Minimum number of enrolled and injected subjects		
1 month to $<$ 2 years	1		
2 to <6 years	3		
6 to <12 years	3		
12 to <18 years	3		

Table 2.Minimum enrollment per age group

The first three subjects between the ages of 2 to 17 will be recruited and injected. Once these three subjects have completed the Day-8 safety evaluation, enrollment will be put on hold until the Data Safety Monitoring Committee (DSMC) reviews all available safety information and agrees to proceed with additional enrollment. If the DSMC concurs, study enrollment will then be open to all age cohorts (1 month to <18 years). The DSMC will then determine the frequency to meet based on review of the available trial information.

4.3 Withdrawal

In accordance with the Declaration of Helsinki, each subject is free to withdraw from the study at any time and without providing a reason.

A subject who withdraws consent prior to arrival at the study site on Day 1 will be considered a screen failure.

Should a subject withdraw after administration of the investigational product all efforts will be made to complete and report the observations up to the time of withdrawal as thoroughly as possible. An explanation should be given of why the subject is withdrawing or being withdrawn from the study.

The investigator may withdraw a subject from the study at any time at the discretion of the investigator for any of the following reasons:

• A protocol violation occurs.

- A serious or intolerable adverse event (AE) occurs.
- A clinically significant change in a laboratory parameter occurs.
- At the investigator's/sponsor's discretion as long as it is in the best interest of the subject.
- The sponsor or investigator terminates the study.
- The subject or parent/guardian requests to be discontinued from the study.

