Clinical Trial Protocol: NAV3-18

Study Title:	A Prospective, Open-Label, Multicenter Study of Lymphoseek® as a Lymphoid Tissue Targeting Agent in Pediatric Patients With Melanoma, Rhabdomyosarcoma, or Other Solid Tumors Who Are Undergoing Lymph Node Mapping
Study Number:	NAV3-18
Study Phase:	2
Product Name:	Lymphoseek®
IND Number:	061757
Investigators:	Multicenter
Sponsor:	Cardinal Health 414, LLC [name]
Sponsor Contact:	
Medical Monitor:	

	Date
Original Protocol:	24 April 2015
Amendment 1:	14 August 2015
Amendment 2:	18 January 2016
Amendment 3:	11 January 2017
Amendment 4:	01 September 2017

Confidentiality Statement

This document and its contents are the property of and confidential to Cardinal Health 414, LLC. Any unauthorized copying or use of this document is prohibited

SYNOPSIS

Study title	A Prospective, Open-Label, Multicenter Study of Lymphoseek [®] as a Lymphoid Tissue Targeting Agent in Pediatric Patients With Melanoma, Rhabdomyosarcoma, or Other Solid Tumors Who Are Undergoing Lymph Node			
	Mapping			
Study phase	Phase 2			
Study objective(s)	 Primary: To evaluate safety and tolerability of Lymphoseek in pediatric subjects with melanoma, rhabdomyosarcoma, or other solid tumors who are undergoing lymph node mapping. Secondary: To assess the identified lymph node(s) to confirm: the presence/absence of tumor metastases; agent localization per tumor type; degree of localization (nodes per subject both intraoperatively and with preoperative SPECT). To determine the concordance of in vivo localization rates of Lymphoseek and LymphazurinTM, a vital blue dye (VBD), in tissue excised and histologically confirmed as lymph nodes from those subjects receiving two mapping agents. To record the change of subject stage based on histopathology and make a descriptive assessment on change in treatment plan 			
Study drug	Lymphoseek®			
Dose(s)	50 µg Lymphoseek radiolabeled with 18.5 MBq (0.5 mCi) 99m Tc			
Route of administration	For subjects with melanoma, Lymphoseek will be administered as 1, 2 or 4 intradermal, peritumoral injections or around the excision biopsy site. For subjects with rhabdomyosarcoma or other solid tumor type, Lymphoseek will be administered as intradermal peritumoral injection(s) if anatomically appropriate or, if not possible, injection should be performed as determined clinically appropriate by the surgeon.			
Duration of treatment	It Single administration			

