8.1.1 Demographic and Other Baseline Characteristics

Male or female pediatric subjects aged <18 years (at least 20 of the subjects will be ≤ 16 years of age) will be enrolled. For the primary analysis, at least 27 subjects will be injected with Lymphoseek. This population of subjects will include at least 6 subjects with melanoma, at least 6 subjects with rhabdomyosarcoma, with enrollment open to up to an additional 15 subjects with other solid tumors for which ILM and SLNB are appropriate. At least 25 subjects will complete the 4-to 14-day follow up.

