8.7 Safety

8.7.1 Adverse Events

8.7.1.1 Definition of Adverse Event

The definitions below follow International Conference on Harmonization (ICH) – Good Clinical Practice (GCP) (see also ICH Guideline for Clinical Safety Data Management: Definitions and Standards for Expedited Reporting).

Adverse Event (AE)

An AE is defined as any untoward medical occurrence in a subject administered a pharmaceutical product and which does not necessarily have a causal relationship with this treatment. An AE can therefore be any unfavorable and unintended sign (including an abnormal laboratory finding), symptom, or disease temporally associated with the use of a medicinal (investigational) product, whether or not considered related to the medicinal (investigational) product.

By definition for this study, all untoward medical occurrences beginning on the day of injection through the 4- to 14-day follow-up assessment are to be reported as AEs. Additionally, untoward medical events occurring prior to the day of injection will only be captured as AEs if they are related to a study procedure. SAEs will be reported from the time of consent through the end of participation. All adverse events should be followed until resolution or stabilization as determined by the investigator.

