9.8 Handling of Missing Data

There will be no missing value imputation used in this study. All endpoints will be analyzed with subjects who have non-missing data (i.e., a complete case analysis).

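### After a single dose, Section 4.3 lets safety-triggered withdrawal from the study cut short the collection of new safety data, and it does not agree with the follow-up duties stated elsewhere

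*Combined protocol and SAP*

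**What the plan says.** The Synopsis gives the duration of treatment as "Single administration". Section 4.3 says: "The investigator may withdraw a subject from the study at any time at the discretion of the investigator". The listed reasons include a protocol violation, "A serious or intolerable adverse event (AE) occurs" and "A clinically significant change in a laboratory parameter occurs". The list does not separate the time before injection from the time after it, nor stopping treatment from leaving the study. For a subject who leaves after the product has been given, the stated effort is to "complete and report the observations up to the time of withdrawal". Section 10.6.2 refers back to these criteria.

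Other sections bear on what happens next:
- Section 8.7.1.1: "All adverse events should be followed until resolution or stabilization as determined by the investigator". The same section ends serious AE reporting when participation ends.
- Section 8.8.2 requires repeat testing of a clinically significant laboratory change until it returns to baseline or is explained.
- Section 8.7.2.3 ties follow-up of an ECG finding that became an AE to the subject's participation.
- Section 9.9.3 ends AE observation at termination from the study.
- Section 9.8 rules out imputation: "All endpoints will be analyzed with subjects who have non-missing data (i.e., a complete case analysis)".
- Section 8.1.1: "At least 25 subjects will complete the 4-to 14-day follow up".

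**The concern.** The primary objective is safety and the primary safety variable is AE incidence (Sections 2.1 and 9.4.1). When dosing is repeated, withdrawal for an AE can at least limit further exposure. Here, once the injection has been given, no Lymphoseek exposure remains to be limited. What withdrawal can still do is end observation, and two of the three reasons are themselves safety findings. Whether later data exist for a child can then depend on how that child has fared. New events in these children may go unrecorded, and the Day 4 to 14 vital-sign summaries would rest on the children who were not withdrawn.

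**Working it through.** **1. What withdrawal can still prevent.** Under Section 4.1 a child is enrolled on arrival on the morning of Day 1. Between arrival and injection, withdrawal does prevent exposure. After injection it cannot. Between injection and surgery it could still avoid the optional Lymphazurin.

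**2. What remains to be observed after injection, and whether it survives a Section 4.3 withdrawal.**

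| Item | Section | After withdrawal |
|---|---|---|
| Triggering AE | 8.7.1.1, 9.9.1 | Already recorded; child stays in the safety population; event to be followed, no exception for withdrawn subjects |
| Triggering laboratory change | 8.8.2 | To be retested, no exception stated |
| ECG finding that became an AE | 8.7.2.3 | Follow-up tied to participation |
| New AE | 9.9.3 | Window closes at termination from the study |
| New serious AE | 8.7.1.1 | Window closes at end of participation |
| After-surgery laboratory tests | 7.2.8 | Lost only if withdrawal precedes that draw |
| Day 4 to 14 vital signs, examination, AE review | 7.2.9 | Not required by Section 4.3 |

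No section says whether the duties in the first two rows continue after withdrawal, and none requires the items in the last four.

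**3. The laboratory reason.** Blood is scheduled once before injection and once after surgery (Section 7.2.1, Table 11, Appendix 1). Among scheduled tests, a change can therefore first show at the after-surgery draw. The main scheduled assessment still to come is the Day 4 to 14 visit, which is what withdrawal at that point would drop.

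**4. Size.** Section 9.7 gives no power or precision calculation, so only the counts can be reproduced: 6 + 6 + 15 = 27. With exactly 27 injected and 25 completing, 27 − 25 = 2 children (2/27 = 7.4%) lack the last visit.

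Precision is barely affected. With zero events, the one-sided 95% upper bound is 1 − 0.05^(1/n):
- n = 27: 10.5%
- n = 25: 11.3%

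Selective loss matters more. Assume, for illustration, that w withdrawn children each have a further, unrecorded AE of a given type and that no other child has it. The record then shows 0/27 (exact two-sided 95% interval 0 to 12.8%). The true figures would be:
- w = 1: 1/27 = 3.7% (0.1 to 19.0%)
- w = 2: 2/27 = 7.4% (0.9 to 24.3%)
- w = 3: 3/27 = 11.1% (2.4 to 29.2%)

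The documents give no expected number of such withdrawals, so w from 1 to 3 is an assumed range.

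**The case against.** The strongest reply is that the rule is discretionary and the rest of the protocol largely contains it. Much of this stands, and it rules out several stronger readings that a reader might infer.

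- *Withdrawal ends safety observation altogether.* Not supported. Sections 8.7.1.1 and 8.8.2 require follow-up of the triggering AE or laboratory change without exempting withdrawn subjects.
- *Overall AE incidence is lowered by withdrawing children with AEs.* Not supported. Such a child already counts as having an AE and stays in the safety population. Under Section 8.8.2 a clinically significant laboratory change that is not a laboratory error is itself an AE. Complete-case analysis does not remove recorded events. Only additional, later events can be missed.
- *Follow-up laboratory summaries are biased.* No laboratory tests are scheduled at Day 4 to 14, and a withdrawal prompted by the after-surgery draw cannot lose that draw.
- *Withdrawn children are never replaced.* Section 4.4 replaces those who do not reach surgery or mapping. Replacement restores the count but not the missing observations.
- *A third loss breaks the completer target.* The Synopsis and Section 8.1.1 say at least 27, and Section 9.7 says approximately 27. Further enrollment can restore 25 completers.
- *Every trigger biases in the product's favour.* A protocol violation also shortens observation, but it is not tied to how the child is doing, so selective loss is not shown for that reason.

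It can also be said that the sentence on data after dosing concerns families who choose to leave. Its opening suggests so, but the next sentence also covers subjects who are withdrawn by others, so its scope is ambiguous.

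What the reply does not answer is that new AEs, new serious AEs and the Day 4 to 14 assessments have no stated protection after an investigator-initiated withdrawal. The target of 25 completers limits how many children are lost, not which ones.

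**Conclusion.** The point holds in a limited form. After injection, withdrawal under Section 4.3 cannot reduce Lymphoseek exposure. It can truncate collection of new AEs and serious AEs and drop the Day 4 to 14 vital signs, examination and AE review, preferentially in children with a safety finding. The possible bias is confined to additional later events and those follow-up assessments, over at most 14 days. Nothing is imputed, and replacement does not recover the data. Each unrecorded later event of a given type in a separate child is worth 3.7 percentage points at n = 27. Whether any bias arises depends on how often investigators use the discretion and on whether withdrawn children have further events; the documents inform neither. This is a rule worth correcting, not a defect that undermines the primary analysis.

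**What to change.** In Section 4.3, state that once Lymphoseek has been given, an AE, a laboratory change or a protocol violation does not by itself end safety data collection. The after-surgery laboratory tests, the Day 4 to 14 assessments and AE and serious AE collection continue, unless consent or assent for follow-up is withdrawn or the existing ground of the subject's best interest applies. Before injection the listed reasons can stand as they are. Clarify that the limit on observations after dosing applies only where one of those two exceptions ends follow-up.

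Reconcile Sections 8.7.1.1, 8.7.2.3, 8.8.2, 9.9.3 and 10.6.2 with this, so that the AE, serious AE, ECG and laboratory follow-up windows no longer close merely because one of the three reasons was invoked. The change concerns data collection only and leaves decisions about the child's care untouched.

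The cost is protocol wording and keeping these children on the existing visit schedule. No visit or procedure is added.
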